## **7.5 SECONDARY OBJECTIVE ANALYSIS**

### **7.5.1 Key secondary objective analysis**

This section is not applicable as no key secondary endpoints were specified in the protocol.

### **7.5.2 Secondary objective analysis**

Data from participants assigned to the quetiapine arm will not be included in the analysis models for the secondary endpoints.

#### **7.5.2.1 MADRS response**

Response is defined as  $\geq 50\%$  reduction in MADRS total score from baseline to a specific post-baseline visit (Visit X), where percent reduction from baseline at Visit X is calculated as:

$$\% \text{ reduction} = \frac{(\text{MADRS total score at baseline} - \text{MADRS total score at Visit X})}{\text{MADRS total score at baseline}} * 100$$

The proportions of participants achieving response for each analysis visit up to Week 6 (Visit 8/EOT) will be summarized as the frequency and percentage of participants in each treatment arm.

To handle missing data when analyzing MADRS response, multiple imputation and logistic regression modeling will be used. Specifically, missing data will first be multiply imputed using fully conditional specification methods (12, 13). Specifically, a regression model will first be used for imputation, including baseline MADRS total score and MADRS total score at each post-baseline timepoint by treatment, to fill in missing values for MADRS total score for all timepoints. These filled-in values will serve as starting values for the next step, which is to use the regression method to complete the imputation in each dataset. This process will be repeated to create 100 imputed datasets where for each one, a binary variable for response up to week 6 will be created using the imputed values of MADRS total score at baseline and up to week 6. The seed to be used for the multiple imputation step is '14020011'.

MADRS response up to week 6 will be analyzed in each imputed dataset using a logistic regression model, including the fixed categorical effects of treatment and baseline MDD severity. The results will then be combined using Rubin's rule to obtain pooled estimates of the population odds ratio (OR), and associated confidence intervals and p-values, for each active treatment arm versus placebo. Response at week 6 is the defined secondary endpoint but the other analysis visits will be displayed as well.

Please see [Section 10.1.4](#) for SAS code to implement the multiple imputation procedure described above.

#### 7.5.2.2 Other secondary endpoints

For changes from baseline at Week 6 in (i) STAI State and Trait version scores, (ii) CGI-S score, and (iii) SMDSS total score, an MMRM model like that described for the primary endpoint analysis in [Section 7.4.1](#) (replacing the fixed continuous effect of baseline MADRS total score at each visit with baseline value of the specified score at each visit) will be used to obtain the adjusted change from baseline at Week 6 for each of the BI active arms versus placebo.

Descriptive statistics for observed and change from baseline values at Week 6 will be presented by treatment arm, including the quetiapine arm. For STAI State and Trait Anxiety, CGI-S, and SMDSS, the frequency and proportion of participants reporting each response category at baseline and at Week 6 will also be displayed.

Proprietary confidential information © 2023 Boehringer Ingelheim International GmbH or one or more of its affiliated companies.

A series of black horizontal bars of varying lengths and positions on a white background, suggesting a redacted document. The bars are irregular in shape, with some having sharp ends and others being more rounded. They are positioned in a staggered, non-overlapping manner across the page.

This figure displays a 10x10 grid of black and white bars, representing a 2D convolutional feature map. The bars are arranged in a grid pattern, with varying widths and heights. Some bars are solid black, while others are white with black outlines. The overall pattern is a dense, abstract representation of data.

The image consists of a series of horizontal black bars of varying lengths and positions, set against a white background. The bars are irregular in shape, with some having sharp edges and others being more rounded. They appear to be arranged in a grid-like pattern, but with missing or overlapping elements. The overall effect is one of a heavily redacted or processed document, where the original text has been completely obscured by black ink.

## 7.7 EXTENT OF EXPOSURE

Extent of exposure will be calculated as the difference between last intake of study drug and the first administration of the study drug, plus one day. Descriptive statistics will be provided for number of days of exposure for each treatment arm. Also, cumulative exposure of number and percentage (N, %) of patients will also be displayed as “< 1 week”, “1 to < 2 weeks”, “2 to <3 weeks”, “3 to <4 weeks”, “4 to <5 weeks”, “5 to <6 weeks”, “6 weeks” or “>6 weeks”.

## **7.8 SAFETY ANALYSIS**

All safety analyses will be performed on the TS. Adverse events (AEs) will be coded based on the most current version of MedDRA. Analyses will be performed as defined in CTP Section 7.2.5.

### **7.8.1 Adverse Events**

The analyses of AEs will be descriptive in nature. All analyses of AEs will be based on the number of patients with AEs and not on the number of AEs. The reporting and analyses of AEs will follow the BI guideline ([14](#)).

For further details on summarisation of AE data, please refer to ([7](#), [14](#)).

The analysis of AEs will be based on the concept of treatment emergent adverse events. Thus, all AEs occurring between the date of the first administration of trial treatment through the date of the last administration of trial treatment + residual effect period, a period of 28 days after the last dose of trial medication, will be assigned to the on-treatment period for evaluation. AEs that start before first drug intake and deteriorate under treatment will also be considered as 'treatment-emergent'. Adverse event data will be summarized by treatment taken at the onset of the event. AEs that occur before first drug intake will be assigned to 'screening', and adverse events that occur within 28 days after the residual effect period will be assigned to 'follow-up' (for listings only).

For details on the treatment definitions, see [Section 6.1](#).

#### Adverse events of special interest (AESIs)

A hepatic injury is defined by the following alterations of hepatic laboratory parameters:

- An elevation of AST and / or ALT  $\geq$  3-fold ULN combined with an elevation of total bilirubin  $\geq$  2-fold ULN measured in the same blood draw sample; and / or
- Marked peak aminotransferase (ALT and / or AST) elevations  $\geq$  10-fold ULN.

Refer to CTP Section 5.3.6.1.4 for details.

#### Other significant AE (according to ICH E3)

According to ICH E3 ([15](#)), AEs classified as "other significant" needs to be reported and will include those non-serious and non-significant AEs with

1. Action taken = 'discontinuation' or action taken = 'reduced'; or
2. Marked hematological and other lab abnormalities or lead to significant concomitant therapy as identified by the Clinical Monitor / Investigator during medical quality review at TOM.

#### AE summaries

An overall summary of adverse events will be presented. The frequency of patients with adverse events will be summarized by treatment taken at the onset of the event, primary system organ class (SOC) and preferred term (PT) according to MedDRA. The SOCs will be sorted by default alphabetically and PTs will be sorted by frequency within an SOC. Separate tables will be provided for patients with:

- drug-related AEs
- serious AEs
- serious related AEs
- AESIs
- other significant AEs (according to ICH E3)
- AEs leading to death
- AEs leading to discontinuation of trial medication
- AEs occurred with incidence in the preferred term >2%
- AEs occurred with incidence in the preferred term >5%
- AEs occurred during the follow-up period
- Extrapiramidal AEs (AEs in the 'extrapiramidal syndrome' SMQ and all of its sub-SMQs (akathisia, dyskinesia, dystonia, and Parkinson-like events)).

#### AEs suggestive of abuse potential

In support of an evaluation of human abuse potential, user-defined AE categories (UDAEC) are defined in [Section 10.2](#). In addition, frequency of patients with AEs suggestive of abuse potential will be summarized by treatment, UDAEC, and PT. A listing of the AEs and a listing of patients with >100% compliance or unreturned medication kits will also be provided.

#### **7.8.2      Laboratory data**

The analyses of laboratory data will be descriptive in nature and will be based on BI standards ([16](#)). Only patients with at least one available on-treatment value will be included in the analysis of an individual laboratory parameter. All individual data will be presented in listings. Study visits will be presented by the Visit labels in [Table 6](#).

#### **7.8.3      Vital signs**

Only descriptive statistics are planned for this section of the report. In case of multiple measurements including unscheduled visits, the value for the vital sign measurement will be the average of all the measurements for the corresponding visit.

#### **7.8.4      ECG**

12-lead ECG measurements will be assessed as described in the CTP Flow Chart. 12-lead ECG-findings before first intake of trial drug will be considered as baseline condition, or as

AEs (during the trial) if judged clinically relevant by the investigator and will be analyzed as such. No quantitative analysis of these ECG data will be prepared. For ECG-related AEs, all qualitative findings will be listed per patient.

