### **2.2.3        Safety**

There are no safety end points defined for this trial; however, safety will be assessed descriptively in participants who received at least one dose of trial drug (e.g., AEs, SAEs, AESI, extrapyramidal AEs, C-SSRS, physical examination, vital signs ECG and laboratory tests).

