### 5.3.4      **Electrocardiogram**

The 12-lead ECGs will be performed as scheduled in the [Flow Chart 1](#). Twelve-lead ECGs (I, II, III, aVR, aVL, aVF, V1 – V6) will be recorded using equipment provided by a central ECG vendor. The ECGs will be recorded for at least 10-second duration after the participants have rested for at least 5 minutes in a supine position and prior to lab sampling. Electrode placement will be performed according to the method of Einthoven/Goldberger (ankles and wrists). At all time points indicated in the [Flow Chart](#), single ECGs will be recorded. ECG recordings at planned time points may be repeated for quality reasons like alternating current artefacts, muscle movements and electrode dislocation. In this case the repeated ECG recordings will be used if quality was better.

The investigator or a designee will evaluate whether the ECG is normal or abnormal and whether it is clinically significant, if abnormal. The electronic version of the ECG is regarded as source data. Dated and signed printouts will be stored in the participant's medical file if there is no validated and certified e-medical record for ECG data.

Additional ECGs may be collected by the investigator for safety reasons. Clinically relevant findings noticed at baseline assessment (Visit 1) should be reported as baseline condition.

Clinically relevant abnormal findings noticed after baseline assessment will be reported as AEs and followed up and/or treated locally until normal or stable condition.

All ECGs will be transmitted electronically to the central ECG vendor in order to enable a centralized and independent re-evaluation of all 12-lead ECGs. A centralized and independent re-evaluation will be done. Abnormalities detected during this centralized ECG evaluation will not necessarily qualify as AE.

Central evaluation on individual ECG level will be performed by the vendor and a report will be provided to the site. Decisions on eligibility for the trial and treatment or further follow-up of any findings are in the responsibility of the investigator.

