## 7.2 PLANNED ANALYSES

### 7.2.1 General considerations

All data will be listed and summarized by treatment group using appropriate methods. For continuous data, the number of observations, mean, standard deviation (SD), minimum, median and maximum will be provided. The frequency and proportion of participants in each category will be presented for categorical data.

Analysis sets defined for this trial include the full analysis set (FAS) and the treated set (TS). The FAS comprises all randomized participants who received at least one dose of trial medication during the trial and had a baseline observation recorded. Unless otherwise specified, efficacy analyses will be performed on the FAS and will be based on assigned treatment. Full specifications for the FAS will be provided in the TSAP.

Safety analyses will be conducted on the TS, which includes all randomized participants who have received at least one dose of the trial medication. Safety analyses will be conducted using actual treatment received. Data from participants who were screened but not randomized will be listed but not included in any summaries or inferential statistics.

Important protocol deviations (iPDs) will be collected throughout the trial conduct and will be summarized in the CTR as defined in the iPD specification document.

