## **7. PLANNED ANALYSIS**

The format of the listings and tables will follow the BI guideline "Standards for Reporting of Clinical Trials and Project Summaries" (9).

The individual values of all patients will be listed, sorted by dose group, patient number and visit. AE listings will be sorted by assigned treatment (see [Section 7.8.1](#) for details). The listings will be contained in an Appendix of the CTR.

For End-Of-Text tables, the set of summary statistics is: N / Mean / Standard Deviation (SD) / Min / Median/ Max. For tables that are provided for endpoints with some extreme data, median, quartiles and percentiles are preferred to mean, standard deviation, minimum and maximum. In general, means, medians, and percentiles are presented to one more decimal place than the raw data and SDs are presented to two more decimal places than the raw data. Minima and Maxima are presented to the same number of decimal places as the raw data.

Disposition of the patient population participating in the trial will be analyzed by treatment and presented by the categories in the standard CRF groups and presented in the clinical trial report as a frequency-distribution.

For categorical data, tabulations of frequencies will include all defined categories even if there is no count in a category. Tabulations of frequencies will display the number of observations in a category as well as the percentage (%) relative to the number of patients in the respective treatment group. All patients in the respective patient set are used whether they have non-missing values or not, unless otherwise specified. Percentages will be rounded to one decimal place. The category missing will be displayed only if there are missing values.

If applicable, conversion from days to weeks, months and years will be as follows:

- weeks = days  $\div$  7
- months = 12  $\times$  days  $\div$  365.25
- years = days  $\div$  365.25.

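### The SAP rules out any quantitative ECG analysis, although the protocol promises by-arm summaries of all data; readable text plans no by-arm summary of ECG intervals

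*SAP*

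**What the plan says.** SAP 7.8.4 treats ECG findings as baseline conditions, or as adverse events when the investigator judges them clinically relevant. For ECG-related adverse events, qualitative findings are listed per patient. On the measurements themselves it says: "No quantitative analysis of these ECG data will be prepared".

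Protocol 7.2.1 sets the general rule: "All data will be listed and summarized by treatment group using appropriate methods". Its next sentence reads: "For continuous data, the number of observations, mean, standard deviation (SD), minimum, median and maximum will be provided". Protocol 2.2.3 states that safety will be assessed descriptively and gives as examples, among others, "physical examination, vital signs ECG and laboratory tests".

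Protocol 7.2.5 is the dedicated safety-analysis section, and SAP 7.8 says safety analyses follow it. It does not name ECG. It does provide that other safety-relevant data will be assessed for possible change from the findings before treatment.

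Some handling of ECG exists. SAP section 7 provides a general listing: "The individual values of all patients will be listed, sorted by dose group, patient number and visit". SAP 7.8.1 provides adverse event tables: "The frequency of patients with adverse events will be summarized by treatment taken at the onset of the event". Protocol 5.3.4 sends every ECG to a central vendor for independent re-evaluation, but adds: "Abnormalities detected during this centralized ECG evaluation will not necessarily qualify as AE".

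**The concern.** The SAP sentence is a stated rule, not a detail left open. Following it removes from the report an output that the protocol's general rule promises. Laboratory data (SAP 7.8.2) and vital signs (SAP 7.8.3) both get descriptive analyses. ECG is the one safety measurement for which the readable SAP forbids a quantitative one.

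The stake is dose selection. The trial compares four doses of BI 1358894 with placebo, and protocol 7.2.2.1 says safety will be taken into account in selecting target doses. A small average shift in an interval across doses is hard to see in a patient-level listing and would rarely be called an adverse event in any one patient. That last sentence is statistical reasoning, not something the documents state.

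**Working it through.** The plan gives no figure to reproduce. The check is a comparison of passages, followed by simple arithmetic on scale.

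**Where each kind of ECG information goes in the readable plan**

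| ECG information | Listing by patient | By-arm summary |
|---|---|---|
| Findings before first dose, handled as baseline conditions | Yes | Yes, concomitant diseases by treatment (SAP 7.2) |
| Findings reported as adverse events | Yes | Yes (SAP 7.8.1) |
| Central abnormalities not reported as adverse events | If in the database | None found |
| Interval values (QTcF, heart rate) and their change from baseline | If in the database | None found; barred by SAP 7.8.4 |

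**Reading the passages together**

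1. ECG intervals are continuous data. Protocol 7.2.1 requires data to be listed and also summarised. SAP section 7 supplies the listing. SAP 7.8.4 rules out the summary.
2. The reference to appropriate methods in protocol 7.2.1 gives latitude on how to summarise. It does not cancel the requirement to summarise, and the next sentence names the statistics.
3. Protocol 7.2.5 specifies no by-arm ECG table. If ECG counts as other safety-relevant data, that section calls for assessment of change from pre-treatment findings. The specific bar in SAP 7.8.4 would override this for any numerical output.
4. Protocol 2.2.3 is softer support, because by-arm counts of ECG-related adverse events could pass as a minimal descriptive assessment.
5. SAP section 4 lists changes from the protocol. None of its four readable bullets mentions ECG. A fifth is redacted.
6. Data availability is unclear. Protocol 5.3.3 states that the central laboratory transfers its results to the sponsor. For ECG, protocol 5.3.4 states only: "Central evaluation on individual ECG level will be performed by the vendor and a report will be provided to the site".

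**Scale**

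- Flow Chart 1 schedules ECGs at Visits 1, 2, 4, 6 and 8, at early EOT and at Visit 9. About 431 participants are to be randomised (synopsis). With full attendance, Visits 4, 6 and 8 give 431 × 3 = 1,293 ECGs. Adding Visit 9 gives 431 × 4 = 1,724. Early EOT and unscheduled recordings are not counted.
- Adverse event counts are a coarse screen at these arm sizes. With zero events among n participants, the one-sided 95% upper bound for the true rate is 1 − 0.05^(1/n). For n = 41 (5, 25 or 75 mg) this is 7.0%. For n = 82 (125 mg) it is 3.6%. These bounds hold for any adverse event in arms of this size and are not specific to ECG.

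**The case against.** The strongest case against is that the conflict rests on one sentence under general considerations, while the section written for safety, protocol 7.2.5, sets out tables for adverse events and laboratory data and does not name ECG. It also relies on sponsor reporting standards that the reader cannot see. Physical examination stands beside ECG in protocol 2.2.3 and has no readable SAP summary either, so the treatment of ECG may be a reporting convention. Every ECG is reviewed by the investigator and re-read centrally, and an independent DMC reviews safety data (protocol 3.2 and 8.7). If central intervals never reach the sponsor, there is no continuous ECG variable to summarise.

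Parts of this stand. The clash is clear only with protocol 7.2.1; protocol 7.2.5 and 2.2.3 support it less strongly. The data-transfer question is open and decides which remedy applies. The rest does not remove the point. Silence on physical examination differs from an explicit prohibition on numerical data. Review of single ECGs does not show an average shift between arms. The readable description of the DMC's data names SAEs, AEs and laboratory data, not ECG intervals.

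A reader might infer more: that ECG is left out of the analysis altogether, that the sponsor made an undeclared departure from the protocol, or that a QT problem is being kept from view. The documents support none of these. Listings and adverse event tables cover part of the ECG information. The redacted bullet in SAP section 4 may declare the change, and further analyses may lie in protocol 7.2.6 or in the redacted parts of SAP 7.5 to 7.8. No readable passage reports a QT signal; QTcF appears in the readable text as an entry criterion (exclusion criterion 22).

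**Conclusion.** The point holds as a conflict between SAP 7.8.4 and protocol 7.2.1, with secondary tension against protocol 7.2.5. As readable, the plan would leave the values of up to 1,293 ECGs at Visits 4, 6 and 8 (1,724 with Visit 9) out of every by-arm summary, together with central abnormalities not called adverse events. The counts assume about 431 randomised and full attendance.

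The consequence is limited to the safety description that informs dose selection. The primary endpoint, the MMRM and the MCPMod analysis are untouched. The conclusion rests on two readings: that the ECG data named in SAP 7.8.4 are all the 12-lead data of that paragraph, and that the redacted text neither declares nor replaces the missing summary. It should be corrected before unblinding, and confidence is medium because of the redactions and the unresolved data transfer. Recordings at each time point are single (protocol 5.3.4), so a descriptive table would not amount to a formal QT assessment.

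**What to change.** Before treatment information is released (SAP section 8), replace the quoted sentence in SAP 7.8.4 with:

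> The ECG intervals available from the central reading (at least QTcF and heart rate) will be summarised descriptively (N, mean, SD, minimum, median, maximum) on the TS by treatment arm and visit, as value and change from baseline.

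The baseline definition in SAP 6.7 can be used as it stands. By-arm counts of central abnormalities, or of QTcF categories fixed before unblinding, are optional. They go beyond what protocol 7.2.1 requires and would serve reporting only, not as a clinical rule.

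The cost is a few tables and their programming, and possibly a data transfer from the central ECG vendor. No new recordings or visits are needed. If the intervals cannot be obtained, state the omission and its reason in SAP section 4 as a departure from protocol 7.2.1, unless the redacted bullet already does so.
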